3.1.3 Definition of Baseline

Baseline is defined as the last value prior to start of dosing with study medication (typically the Day 1 pre-dose value). Renal biopsy for study eligibility could be performed within 12 weeks prior to the Screening Period or during the up to 42 day Screening Period.

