12. Currently using a strong inducer of the cytochrome P450 3A4 (CYP3A4) enzyme, such as carbamazepine, phenobarbital, phenytoin, rifampin, or St. John's wort;
13. Known hypersensitivity to avacopan or inactive ingredients of the avacopan capsules (including [REDACTED] or inability to swallow the capsules;
14. Participated in any clinical study of an investigational product within 30 days prior to screening or within 5 half-lives after taking the last dose; and
15. History or presence of any medical condition (for example, contraindication to local anesthesia required for renal biopsy, or recurring serious infections) or disease which, in the opinion of the Investigator, may place the patient at unacceptable risk for study participation.

Test Product

Avacopan will be administered orally as hard gelatin capsules containing 10 mg avacopan. The avacopan capsules will be supplied to the study centers in plastic bottles containing 180 capsules.

Matching placebo will be administered orally as matching hard gelatin capsules containing no avacopan but inactive ingredients. The placebo capsules will be supplied to the study centers in plastic bottles containing 180 capsules.

Patients will receive one bottle of avacopan or placebo capsules on Day 1 and Weeks 4, 8, 12, and 16, and two bottles at Weeks 20, 26, 32, 38, and 44.

Patients will be asked to take 3 capsules every morning and 3 capsules every evening orally with water, approximately 12 hours after the morning dose, as instructed. Study medication (avacopan or placebo) should be taken preferably with food. If a patient misses a dose, the next dose should be taken as soon as possible. If it is close to the time for their next dose (within 3 hours), the missed dose should not be taken and the next dose should be taken at the regular time.

Duration of Treatment and Observation

Patients will be screened within a period not to exceed 42 days prior to Day 1. The total treatment period is 52 weeks (364 days) and all patients will be followed for 8 weeks (56 days) after the dosing period.

To the extent possible, any adverse events that are deemed study drug-related and are ongoing at discharge will be followed-up to resolution or until a determination is made that the unresolved event is stable. The patient's condition will be evaluated by the Investigator at the end of the clinical trial and appropriate standard of care medical treatment will be provided to all patients as needed.

Safety Assessments

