3.2.3 Safety Population

The Safety Population will include all subjects who are randomized and have received at least one dose of study drug, including all subjects who have not yet completed the Week 26 visit. All

safety data will be analyzed using the Safety Populations according to the actual treatment received.

Notations for Treatment Periods

Treatment Period A: Initial 26-week placebo-controlled, double-blind treatment period, Day 1 – Week 26

Treatment Period B: Week 26-Week 52, the Avacopan treatment period plus 8 Weeks of Followup, Week 26 to End of Study (EOS)

3 Safety Populations for this study:

- 1. The Safety Population in the Treatment Period A is defined as all subjects who received at least one dose of blinded Investigational Drug during Treatment Period A.
- 2. The Safety Population in Treatment Period B is defined as all subjects who received at least one dose of Avacopan during Treatment Period B.
- 3. The All Avacopan Treated Population is defined as all subjects who received at least one dose of Avacopan in the study.

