6.4 Safety Laboratory Parameters

Laboratory parameter results and changes from baseline will be summarized by visit. Summaries will be limited to values assessed at the Central Laboratory. Laboratory values collected at local laboratories will be provided in listings, but not summarized. Shift tables from baseline to subsequent study visits will also be generated based on the Central Laboratory measurements for ALT, AST, total bilirubin, serum creatinine, urine protein:creatinine ratio, creatine phosphokinase, sodium, hematocrit, platelets, white blood count, neutrophils, and lymphocytes. Counts and percentages of laboratory values outside the normal reference range will be summarized by laboratory parameter, treatment group and visit. The denominator for percentages will be the number of subjects in the particular treatment group with measurement at a specified visit. Laboratory values outside the reference ranges will be flagged in the listings. Summaries will be presented separately for the double-blind and avacopan treatment periods, respectively.

The subject incidence of elevated laboratory values of ALT, AST, total bilirubin, alkaline phosphatase, creatinine, potassium, and creatine phosphokinase (CPK) as assessed by the Central Laboratory, will be summarized by treatment group and Grade, as defined per Common Terminology Criteria for Adverse Events (CTCAE) Version 5. Shift from baseline to highest CTCAE grade during the study period will also be produced for these laboratory parameters based on the Central Laboratory measurements. The same summary by treatment and CTCAE grade will be produced for subject incidence of low neutrophils, low lymphocytes, low leukocytes, low hemoglobin, and low platelets. Shift from baseline to highest CTCAE grade during the study period will also be produced for these laboratory parameters. A by-subject listing including all data for these laboratory parameters including CTCAE grade for subjects with any abnormality will be provided.

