6.5 Vital Signs

Vital sign results and changes from baseline will be listed and summarized by study visit and treatment group separately for the double-blind and open-label periods.

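### Laboratory and vital-sign change and shift tables for the avacopan period measure placebo-to-avacopan switchers against a pre-placebo value; a first-avacopan-dose baseline should be added

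*SAP*

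**What the plan says.** SAP 3.1.3 states "Baseline is defined as the last value prior to start of dosing with study medication (typically the Day 1 pre-dose value"), and Protocol 8.7 carries the same definition. The protocol synopsis, under Test Product, shows that the term covers both arms: "Study medication (avacopan or placebo) should be taken preferably with food".

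Three kinds of safety table use this baseline:

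- **Laboratory change (SAP 6.4):** "Laboratory parameter results and changes from baseline will be summarized by visit".
- **Laboratory shifts (SAP 6.4):** "Shift tables from baseline to subsequent study visits will also be generated based on the Central Laboratory measurements", for a list that includes ALT, AST, CPK, white cells, neutrophils and lymphocytes. In addition, "Shift from baseline to highest CTCAE grade during the study period will also be produced for these laboratory parameters".
- **Vital signs (SAP 6.5):** "changes from baseline will be listed and summarized by study visit and treatment group separately for the double-blind and open-label periods".

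On periods, SAP 6.4 adds: "Summaries will be presented separately for the double-blind and avacopan treatment periods, respectively". SAP 3.2.3 and 6.1 assign safety data by the treatment actually received, which in Period B is avacopan for everyone. SAP 3.2.3 also creates a pooled set: "The All Avacopan Treated Population is defined as all subjects who received at least one dose of Avacopan in the study". No section names a Week 26 or first-avacopan-dose baseline for laboratory values or vital signs. SAP 4.3 describes Period A and Period B enrollees separately but does not redefine baseline.

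**The concern.** Every placebo patient who continues moves to avacopan at Week 26. For these patients, a table headed as the avacopan period but anchored before the first placebo dose mixes two exposures. It can err both ways: a change that began and persisted on placebo looks like a change on avacopan, and a change that returned on avacopan can look like none.

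Hepatic enzymes, white cells and CPK are events of special interest in SAP 6.3, and Protocol 12.3.2 says that hematology monitoring and pausing rules were tightened after DMC review. The first weeks after the switch are a placebo patient's first exposure to avacopan, so a reader will look there for a laboratory change. SAP 8.1 also has data beyond Week 26 summarised at the primary data cutoff, so the tables arise in both analyses.

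**Working it through.** The plan states no figure for this point, so there is none to reproduce. The check has three parts.

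**1. How the SAP anchors Period B data**

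| Data | Reference for Period B | Where |
|---|---|---|
| Treatment-emergent adverse events | First dose in each period; first avacopan dose for the All Avacopan Treated set | SAP 6.3 |
| Histologic activity index | Week 26 to Week 52 | SAP 5.2.2 |
| UPCR | Week 26 to later visits, by prior treatment group | SAP 5.3.1.2 |
| Laboratory change and shift | Single baseline before first study dose | SAP 3.1.3, 6.4 |
| Vital-sign change | Single baseline before first study dose | SAP 3.1.3, 6.5 |

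Among these, the last two rows are the exceptions. For the same switcher, adverse events are counted from the first avacopan dose while laboratory change is counted from before placebo.

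**2. What the tables show for a switcher**

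Write X0 for the value before the first study dose, X26 for the value before the first avacopan dose, and Xv for a later visit. Then

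Xv − X0 = (X26 − X0) + (Xv − X26).

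The first bracket arose on placebo, the second on avacopan. The Period B table shows the sum. Three patterns for a graded parameter:

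| Day 1 → Week 26 → Period B visit | Shift shown under the SAP | Shift from first avacopan dose |
|---|---|---|
| Grade 0 → 1 → 1 | 0 to 1 | 1 to 1 (none) |
| Grade 1 → 0 → 1 | 1 to 1 (none) | 0 to 1 |
| Grade 0 → 1 → 0 | 0 to 0 (none) | 1 to 0 |

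The third row marks the limit: a placebo change that has resolved by the Period B visit does not carry over.

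**3. Timing and scale**

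Placebo lasts 182 days (Protocol 3.4). With the scheduled study days in the Time and Events Table, the placebo share of a switcher's baseline-to-visit interval is 182 / (study day − 1):

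| Visit | Study day | Share |
|---|---|---|
| Week 28 | 197 | 182/196 = 93% |
| Week 32 | 225 | 182/224 = 81% |
| Week 38 | 267 | 182/266 = 68% |
| Week 44 | 309 | 182/308 = 59% |
| Week 52 | 365 | 182/364 = 50% |

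These are shares of elapsed time, not estimates of bias.

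For relative changes, let d be the change on placebo to Week 26 and e the change on avacopan afterwards. The table shows (1 + d)(1 + e) − 1. The documents give neither d nor e, so the following values are assumptions. With e = 0, d of 5%, 10%, 20% or 30% is shown as +5%, +10%, +20% or +30%, against 0% from a first-avacopan-dose baseline. With d = 20% and e = 5%, the table shows 1.20 × 1.05 − 1 = +26.0% instead of +5%.

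About 88 patients were planned at 1:1, so at most about 88/2 = 44 could be switchers. The real number is likely to be lower: SAP 3.2.5.2 and 10 call the non-elevated stratum small, and patients who leave before Period B are not in that population.

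**The case against.** The strongest reply is that a common pre-treatment baseline is a legitimate choice for descriptive by-visit tables and that little depends on it. Much of this stands.

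- **The controlled comparison is unaffected.** A reader might infer that the safety objective of avacopan against placebo is compromised. It is not: that comparison is made in Period A, where the baseline is right for both arms. Period B has no placebo arm.
- **Not all placebo change carries over.** A reader might infer that everything that happened on placebo is reported as an avacopan effect. Only net change still present at the Period B visit is carried, and the by-visit output shows Week 26, so the drift can be seen. The Period B tables still do not subtract it.
- **Signals have other displays.** Adverse events are re-anchored. Counts outside the reference range and incidence by CTCAE grade need no baseline, and a by-subject listing gives all data on the graded parameters for anyone with an abnormality. A recurrence missing from the shift table would be in that listing.
- **The highest-grade shift is ambiguous, not shown to be wrong.** A reader might infer that placebo and avacopan peaks are pooled in one cell. SAP 6.4 leaves its study period undefined, but it presents summaries by period, and SAP 3.2.3 defines safety populations by period. A within-period reading is at least as natural.
- **Replacing the baseline would create its own problem.** At Week 28 the switchers' column would show about 2 weeks of change and the avacopan column about 28. That argues for an added display.

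What does not fall is the rule itself. Followed as written, it gives switchers a reference value from before placebo in a table labelled for avacopan, while the SAP uses a later reference for the other Period B data set out above.

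**Conclusion.** The point holds in a limited form. SAP 3.1.3, applied through 6.4 and 6.5, makes Period B change and shift tables for switchers combine change on placebo with change on avacopan, and it can hide a recurrence on avacopan. The same applies to any All Avacopan Treated change or shift table; SAP 3.2.3 implies such tables, although 6.4 does not list them.

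No hypothesis test is affected, and neither are the Period A comparison, adverse event tables, out-of-range counts or listings. The size of the misattribution cannot be computed from the documents, because they give no rate of laboratory change on placebo and no rate of persistence. Any count of misclassified patients would rest on assumed rates. The conclusion rests on reading baseline in 6.4 and 6.5 as the one defined in 3.1.3, the only definition available. It is a worthwhile, cheap improvement to the safety reporting and not a threat to the trial's main results.

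**What to change.** In SAP 3.1.3, 6.4 and 6.5:

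1. For Period B and All Avacopan Treated summaries of laboratory values, CTCAE shifts and vital signs, add a baseline equal to the last available value before the first avacopan dose. For the avacopan group this is the Day 1 pre-dose value. For the placebo group it is normally the Week 26 visit value, or a later one if the randomized period was extended, which SAP 3.1.8 allows for.
2. Keep the existing baseline as a second display.
3. Present Period B by original randomized group.
4. State that the highest-grade shift is computed within each treatment period.

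Two details need care. Protocol 6.11 specifies pre-dose timing at Week 26 for blood samples but not for vital signs, so the vital-sign rule should check timing against the first avacopan dose. SAP 3.1.8 also foresees missed or virtual visits and local laboratory use, and 6.4 excludes local values from summaries. The last central value may therefore predate Week 26 for some patients, which is why the rule should say last available.

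The cost is SAP wording, one derived variable and an extra set of tables. Under the added baseline, the two columns will cover different lengths of follow-up, and a footnote should say so.

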3.1.4 Handling of Missing Data

Dates will be printed in ISO 8601 date format (YYYY-MM-DD). If only year and month are available, date will be displayed as YYYY-MM. If only year, then just YYYY. Dates that are missing because they are not applicable for the subjects are output as "NA", unless otherwise specified.

If data are missing after all efforts made to collect post-baseline C3G Histologic Index data, missing data will be imputed using multiple imputation methods. See Section 5.2.1 and Appendix 12.3 for further details.

No imputation will be performed for missing safety endpoints, including safety laboratory values, vital signs, electrocardiograms, etc.

Adverse events and prior/concomitant medications/procedures with incomplete start or stop dates will be imputed according to the rules stated in Section 12.2.2.

3.1.5 Other Data Handling Approaches

For continuous variables, the estimated mean and median for a set of values will be printed out to one more decimal place than the individual units of measurement, and the standard deviation will be printed out to 1 additional place. P-values will be given with 4 decimals (i.e., 0.xxxx). When a p-value is less than 0.0001, '<0.0001' will be printed.

All fractional numeric values will be printed with a zero to the left of the decimal point (e.g., 0.12, 0.3 etc.). Percentage values will be printed with 1 digit to the right of the decimal point (e.g., 52.3%, 8.9% etc.).

3.1.6 Summary Statistics

Categorical data will be summarized with counts and percentages of subjects. Continuous data will generally be summarized with descriptive statistics including n (number of non-missing values), mean, median, standard deviation, standard error of the mean (SEM), minimum, and maximum.

3.1.7 Evaluation of Site Effect

This is a multi-center study enrolling subjects at sites across North America, Canada and Europe. Site effect will not be evaluated since the number of subjects at each site is expected to be too small.

3.1.8 Adjustments for Potential Impact of COVID-19

COVID-19 pandemic may impact the conduct of the study from different aspects including quarantines, site closures, travel limitations, interruptions to the supply chain for the investigational product, or other considerations if site personnel or trial subjects become infected with COVID-19.

Data fields to capture visit impact due to COVID-19 were added to the database including visit status (visit not completed/in-person visit partially completed/performed virtually), if visit status was due to COVID-19, whether the visit was completed outside of window due to COVID-19 and how or why participation was impacted by COVID-19 (travel restrictions, study site closed, patient chose not to attend site visit, renal biopsy not allowed at site requiring an extended randomized treatment period, patient received COVID-19 diagnosis, lack of study site personnel, lack of home nursing, local labs used instead of protocol-defined central labs and other). The data will be included in listings. Additionally, if a subject discontinued study treatment early or discontinued early from the study due to COVID-19, these data will be summarized as part of subject disposition. Local laboratory data collected due to COVID-19 will be listed.

Adjustments for missing data due to COVID-19 are incorporated into the multiple imputation analyses, completer analyses, per-protocol analyses and sensitivity analyses. Additionally, wider analysis windows are being allowed in order to capture critical data (e.g. renal biopsy data at Week 26 and Week 52) to reduce missing data. See Section 3.1.2 and Section 5 for additional details.

3.2 Analysis Populations

3.2.1 Randomized Population

The Randomized Population will include all subjects who have provided written Informed Consent/Assent and are randomized in the study.

3.2.2 Intent-to-Treat Population

The Intent-to-Treat (ITT) Population will include all randomized subjects who received at least one dose of study medication; subjects with a histologic activity score of 0 at baseline or who are ongoing and have not completed the Week 26 visit will not be included in the ITT population.

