8.1. Patient Populations

8.1.1. Intent-to-Treat Population

For the purposes of data analysis, the ITT Population will include all patients who have provided written Informed Consent/Assent and are randomized in the study.

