8.7. Statistical Analysis Methodology

A statistical analysis plan (SAP).with specific details of all the planned analyses and sensitivity analyses will be generated and approved before unblinding the data for analysis.

All statistical testing will be two-sided, with the Type I error rate at $\alpha = 0.05$.

The efficacy analyses for the efficacy endpoints will be performed in the ITT and PP populations, with the ITT analysis being the primary analysis.

The earliest timepoint at which the primary analysis of the efficacy endpoints can be conducted is when all patients in the elevated stratum have completed at least the Week 26 study visit. Additionally, enrollment for the stratum with C5b-9 levels ≤ 244 ng/ml could terminate early, if patient enrollment in the other stratum (C5b-9 level > 244 ng/mL) reaches target enrollment first. Further, both strata can be analyzed separately and independently. The stratum with elevated levels (primary population) will be analyzed first should the stratum with C5b-9 ≤ 244 ng/ml (secondary population) continue a blinded follow up – further details will be provided in the SAP.

For efficacy analysis, to control for the Type I error rate, a gate-keeping procedure will be applied for the analysis of the primary efficacy endpoint (percent change in C3G Histologic Index for disease activity). The primary endpoint will be tested in the elevated C5b-9 stratum first with a two-sided $\alpha = 0.05$. If this test reaches statistical significance, then the primary endpoint will be tested in the non-elevated C5b-9 stratum with a two-sided $\alpha = 0.05$. If the test in the elevated stratum fails to reach statistical significance, then the test in the non-elevated C5b-9 stratum will not be performed and only performed as an exploratory analysis. The statistical analysis for the secondary endpoint (C3G Histologic Index for disease chronicity) will be tested at a 0.05 α -level only if the primary endpoint in the same stratum reaches statistical significance.

Another analysis will be performed when all patients have completed the study after week 60. Individual patient group assignment will remain blinded to investigators and patients until after the analysis of the data from the second analysis in order to maintain study integrity.

Baseline is defined as the last value prior to start of dosing with study medication (typically the Day 1 pre-dose value).

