5.3.1.1 Primary Analysis

The primary analysis will be based on the ITT population in the elevated C5b-9 stratum (>244 ng/ml). The primary analysis of percent change from baseline (in the form of ratio) in UPCR over 26 weeks will be performed in the subjects in ITT population whose UPCR is abnormal at baseline using a mixed effect model for repeated measures (MMRM) analysis with treatment group, visit, treatment-by-visit interaction and baseline as a covariate. The abnormal UPCR value is defined as UPCR ≥ 0.15 g/g. Subjects will be considered as repeated measure units over visits. Point estimates and corresponding 95% confidence intervals will be estimated for the difference between avacopan and placebo across 26 weeks using a simple contrast from the model.

To alleviate the skewness of the data, UPCR will be log_e-transformed before entering into the MMRM analysis. Least squares mean differences between avacopan and the placebo group in the percent change from baseline to Week 26 log(UPCR) will be back transformed to obtain the estimate for the baseline-adjusted reduction from control in UPCR. Corresponding P-values will also be presented.

In the MMRM model, missing data will not be imputed. Toeplitz covariance matrix will be used to model within-subject variance-covariance structure for the model errors. If the model does not converge using the Toeplitz covariance matrix, AR(1) covariance matrix will be used. If convergence is still not met, then compound symmetry (CS) will be used.

The code used to generate the MMRM analysis will be similar to the following:

```
Note:
TRT01AN = randomized treatment group (numeric): 1=Placebo, 2=Avacopan
VISITN = Visit Number
LR2BASE = Ratio of Visit Value to Baseline Value (log-transformed)
LBASE = Baseline value of response (log transformed)
proc mixed data=lablog;
class SUBJID VISITN TRT01AN(ref='1');
model LR2BASE = TRT01AN VISITN TRT01AN*VISITN LBASE/
solution cl ddfm=kr;
Repeated VISITN / TYPE=TOEP sub=SUBJID;
**use AR(1) if no convergence, then CS;
lsmeans VISITN*TRT01AN / alpha=0.05 cl pdiff slice=VISITN;
ods output LSMeans=LSM
```

5.3.1.2 Secondary Analysis

run;

The same analysis as described for the primary analysis will also be performed for the following:

- Percent change from baseline over 26 weeks during the double-blind treatment period in the combined C5b-9 strata (subjects with elevated C5b-9 blood levels and non-elevated C5b-9 blood levels)

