8 ANALYSIS TIMING

Per the protocol, the earliest time point at which the primary efficacy analysis can occur is when the last enrolled subject in the primary population (subjects in the elevated C5b-9 stratum) has completed the Week 26 visit. The second (follow-up) analysis will be performed when all subjects have completed the full study after Week 60. No Type I error adjustment will be made for the second analysis since the endpoints for the second analysis are different from the first analysis and it is considered to be supportive.

Additionally, enrollment for the stratum with C5b-9 levels \leq 244 ng/ml could terminate early, if subject enrollment in the elevated stratum (C5b-9 level >244 ng/mL) reaches target enrollment first. Further, both strata can be analyzed separately and independently. The stratum with elevated levels (primary population) will be analyzed first should the stratum with C5b-9 \leq 244ng/ml (secondary population) continue a blinded follow up.

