8.1 Week 26 Primary Analysis

The Week 26 Primary Efficacy Analysis will be performed including all subjects who reach Week 26 or discontinued the study by 01-Oct-2020. The data beyond Week 26 will also be summarized for data collected and cleaned at the time of the data cutoff. As of 01-Oct-2020, there are four subjects (2 patients in each of the two C5b-9 stratum) who are ongoing and will not reach Week 26 at the time of data cutoff of the primary analysis. Details of subjects who had major protocol deviations that could affect the primary efficacy outcome will be documented in a memo along with other patient population decisions at the conclusion of blinded data review prior to the data freeze.

The final analysis will be performed when all subjects have completed the full study after Week 60. The final analysis will repeat the primary analysis on all subjects' data, including patients who are ongoing for the week 26 renal biopsies now and enrolled in the future. The final results will be consider as supportive of the primary analysis. All study results will be included in a single Clinical Study Report.

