10 CHANGES FROM PROTOCOL-SPECIFIED STATISTICAL ANALYSES

- The protocol specified 3 analysis populations for the study including the primary elevated C5b-9 population, the non-elevated C5b-9 population and the combined population. Due to the small sample size in the non-elevated C5b-9 stratum, the primary elevated C5b-9 population will remain as the primary population and the two strata combined (including both elevated and non-elevated C5b-9) will be considered the secondary population for analysis. Data from the non-elevated C5b-9 stratum will only be summarized.
- ITT population definition change to exclude subjects who had baseline C3G Histologic Index of activity score of 0.
- Secondary efficacy endpoint order rearranged.

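### SAP 3.2.2 writes the baseline-zero and still-ongoing exclusions into the ITT set itself, so valid data drop out of most other efficacy analyses

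*SAP*

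**What the plan says.** Protocol 8.1.1: "the ITT Population will include all patients who have provided written Informed Consent/Assent and are randomized in the study". Protocol 8.7 has the efficacy endpoints "performed in the ITT and PP populations, with the ITT analysis being the primary analysis".

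SAP 3.2.2 uses the same label for a smaller set. It requires at least one dose, and patients with "a histologic activity score of 0 at baseline or who are ongoing and have not completed the Week 26 visit will not be included". The protocol's definition survives in SAP 3.2.1 as the Randomized Population, but no efficacy analysis is assigned to that set.

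SAP 5.3.1.1 (UPCR) states: "The primary analysis will be based on the ITT population in the elevated C5b-9 stratum (>244 ng/ml"), and narrows this further to "subjects in ITT population whose UPCR is abnormal at baseline". SAP 5.2.1 also uses ITT for activity.

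SAP section 10 lists one change to the population: "ITT population definition change to exclude subjects who had baseline C3G Histologic Index of activity score of 0". It gives no reason and does not mention the dosing or ongoing conditions.

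On timing, SAP section 8 says "the earliest time point at which the primary efficacy analysis can occur is when the last enrolled subject in the primary population" has completed Week 26. SAP 8.1 fixes the cutoff at 01-Oct-2020 and reports that "there are four subjects (2 patients in each of the two C5b-9 stratum) who are ongoing and will not reach Week 26" by then. Those patients enter a final analysis that is labelled supportive.

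**The concern.** Two different exclusions share one population definition, and neither is explained.

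For baseline zero, the natural guess is that percent change has a zero denominator. That would justify leaving the patient out of a relative change in activity. It would not justify removing the same patient's UPCR, eGFR, chronicity, MCP-1 or quality-of-life data, or the absolute change in activity. The last matters most: under SAP 5.2, absolute change becomes the primary endpoint if normality is rejected for percent change but not for change. Patients with valid values would then be missing from the primary test.

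For ongoing patients, a zero denominator explains nothing. They are out because of the cutoff date. SAP 8.1 admits anyone who reached Week 26 or discontinued by that date. Of two patients enrolled equally late, the one who stopped is analysed and the one still in follow-up is not, so inclusion depends on status after randomisation.

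At stake are usable data from randomised, dosed patients in a small trial, and the meaning of the ITT label.

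**Working it through.** **1. How far the exclusions reach**

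| Analysis | Population in the SAP | Defined if baseline activity is 0? |
|---|---|---|
| Percent change in activity to Week 26 (5.2.1) | ITT, stated | No |
| Absolute change in activity (5.2.1) | ITT, stated | Yes |
| Percent change in activity to Week 52 (5.2.2) | Follows the primary method | No |
| Paired comparison of percent changes (5.2.2) | ITT, stated | No |
| UPCR (5.3.1.1) | ITT with abnormal baseline UPCR | Yes |
| eGFR (5.3.2) | As UPCR | Yes |
| Change in chronicity (5.3.3) | As 5.2 | Yes |
| Response of at least 35% (5.3.4) | None named | No rule; a fall from 0 is impossible |
| MCP-1:creatinine (5.3.5) | As UPCR | Yes |
| SF-36 v2, EQ-5D-5L (5.3.6) | As eGFR | Yes |
| Per protocol (3.2.4) | Subset of ITT | Inherits both exclusions |

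The SAP already treats a zero denominator at endpoint level elsewhere. For Week 26 to Week 52, section 5.2.2 restricts only the percent change to patients whose Week 26 score is above zero, and leaves absolute change alone.

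**2. The planned sample size**

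Inputs (Protocol 8.8, SAP 9): difference 35 points, SD 34, two-sided alpha 0.05, power 90%, 22 per group.

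Normal approximation: n = 2 × (1.960 + 1.282)² × 34² / 35² = 19.8, so 20 per group. The exact two-sample t-test needs 21 (power 90.2%). The stated 22 is therefore reproduced to within two patients.

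**3. Power after exclusions in the elevated stratum**

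Assumption: the stratum reaches its target of 44; the SAP gives no actual count. Noncentrality is λ = 35 / (34 × √(1/n₁ + 1/n₂)), with n₁ + n₂ − 2 degrees of freedom.

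| Removed in total | Per group, even split | λ | Power | Power if all from one arm |
|---|---|---|---|---|
| 0 | 22 | 3.41 | 91.5% | – |
| 2 (ongoing only) | 21 | 3.34 | 90.2% | 90.2% |
| 4 | 20 | 3.26 | 88.7% | 88.4% |
| 6 | 19 | 3.17 | 87.0% | 86.2% |
| 8 | 18 | 3.09 | 85.1% | 83.3% |

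The last three rows add an assumed 2, 4 or 6 baseline-zero patients to the two ongoing ones. The documents do not give that number. Each such patient is 1/44 = 2.3% of the target stratum. Losing two of 44 raises the standard error by √(44/42) = 1.024, or 2.4%.

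**4. What a new label would recover**

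Ongoing patients have no Week 26 histology at the cutoff. If they were put back into ITT, Appendix 12.3 would impute Week 26 within arm from disease type, transplant status and baseline, which adds essentially no information. For the primary endpoint, only a later cutoff recovers the loss. For the MMRM endpoints their observed visits are usable now, but follow-up is partial, so 2.4% is an upper figure there.

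**The case against.** **A population-level rationale can be built.** Inclusion criterion 1b requires mesangial or endocapillary hypercellularity, read locally. The central reader scores both lesions, so a central total of 0 means neither was found. Such a patient also cannot improve on the index. This is coherent, but the SAP does not state it. SAP 3.2.4 already provides for eligibility deviations through the per-protocol set.

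**The comparison stays randomised.** A reader might infer that dropping baseline-zero patients biases the treatment effect. The documents do not support that: the score is a pre-treatment value, read by someone blinded to assignment. The exclusion narrows the population and costs precision. The ongoing rule is less neutral because it depends on status after randomisation, but it concerns four patients and nothing shows a direction of bias.

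**The data are not all lost.** The final analysis brings the ongoing patients back, though only as support. Dosed patients remain in the Safety Population, whose shift tables cover UPCR and serum creatinine. This stands for the ongoing patients. The baseline-zero exclusion is permanent for efficacy.

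**The change was partly declared, and the SAP takes precedence.** Both documents let the SAP supersede the protocol's methods, and section 10 declares the baseline-zero change. That stands. The dosing and ongoing conditions are not declared.

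**The reach is partly inferred.** The phrase every efficacy endpoint would go too far: most sections inherit ITT by cross-reference, and 5.3.4 names no population. It would also go too far to say that a zero denominator affects one calculation only, since the table shows several.

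**Conclusion.** The point holds in a limited form. The SAP's ITT is not the protocol's ITT. Its exclusions remove randomised, dosed patients from analyses in which a zero activity baseline makes nothing undefined, including an absolute change that may become the primary endpoint. An undefined percent change is a plausible reading for baseline zero only; the SAP states no reason for either exclusion.

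A reader might infer a serious loss of power. The figures do not support that for the known exclusions: on the assumed 44 patients, power goes from about 91.5% to 90.2%, still at the planned level. It would fall to between 88.7% and 85.1% if 2 to 6 baseline-zero patients were also lost evenly, but that count is an assumption. These figures use a plain t-test without the baseline adjustment in the ANCOVA.

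Sections 8 and 8.1 conflict on timing. The cutoff falls before two elevated-stratum patients reach Week 26, although section 8 waits for the last enrolled patient of that stratum. This should be fixed before database lock; it does not invalidate the trial.

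**What to change.** 1. Define ITT as all randomised patients, as in Protocol 8.1.1. If a dosing condition is kept, declare it in SAP section 10.
2. Apply the baseline-zero exclusion only to relative change in activity: percent change to Week 26 and to Week 52, and the paired percent-change comparison. SAP 5.2.2 already does this for a Week 26 score of 0.
3. In 5.3.4, name the population and count baseline-zero patients as non-responders.
4. Keep baseline-zero patients in absolute change in activity, chronicity, UPCR, eGFR, MCP-1 and quality of life. UPCR keeps its own baseline condition.
5. Include ongoing patients' observed visits in the MMRM endpoints.
6. Reconcile 8.1 with section 8, so that the primary analysis follows Week 26 completion by the last enrolled elevated-stratum patient.

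Items 1 to 5 cost SAP wording and small programming changes. Because a baseline-zero patient cannot improve on the index, items 3 and 4 may somewhat dilute the response rate and the absolute activity difference. Item 6 costs a delay of unknown length: the SAP does not say how far the ongoing patients are from Week 26, and 8.1 also mentions patients still to be enrolled.
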